### 9.2 Hair Sample Collection

Prior to the Month 0 visit, hair collection instructions will be sent to the participant. Instructions will be provided and will be reviewed with the participant at the Month 0 visit. All participants will self-collect (at home) hair samples using a pair of scissors at study enrollment and at three months and will place them in a pre-addressed and prepaid envelope to be sent back to the UCSF HAL. Approximately 50 strands of hair will be collected (less than is lost from the scalp in a day). Home collected hair specimens will be used for measurement of tenofovir, a marker of long-term adherence to PrEP. Participants will send the hair sample via the mail to the UCSF Hair Analytic Lab for analysis. No other analyses will be performed on this sample and it will be destroyed after analysis.

	Screening/ Enrollment	Month 0	Month 3
Assess eligibility	√		
Informed consent	√		
Randomization	√		

### 9.3 Urine Sample Collection and Analysis (Intervention Arm Only)

Prior to the Month 0 visit, urine test kits will be sent to all participants in the intervention arm. Urine samples will be collected by the participant before or during the video visit only for participants in the intervention arm. Urine is collected with a volume of at least 5mL into a

urine collection cup provided to the participant. The urine may be collected at the beginning of the urine stream (no need for clean catch). The participant will be provided instructions on how to complete the urine test, and may discuss any questions with the research coordinator at the time of enrollment/first study visit

The participant will be provided a \$50 cash or gift card reimbursement for completion of all study procedures at each visit, including the survey and urine collection. Reimbursement may be provided via an e-gift card or check.

Hair TFV Levels		√	√
POC Urine Testing (intervention arm only)		√	√
PrEP2-BAY Counseling Intervention (intervention arm only)		√	√
Online questionnaire		√	√

### Device for Tenofovir Testing

We obtained pre-trial consultation advice from the Food and Drug Administration's (FDA's) Center for Devices and Radiological Health (CDRH) regarding the our use of the novel point of care urine tenofovir assay in PrEP2-BAY and verified that the urine tenofovir assay is not Investigational Device Exempt (IDE) because we are returning test results to participants in the intervention arm of the trial. Per FDA regulations (21516 CFR 812), the alternative determinations applicable to our studies are either Nonsignificant Risk (NSR) or Significant Risk (SR). Under FDA 21 CFR 812.3(m), a Significant Risk (SR) device is defined as an investigational device that "Is intended as an implant and presents a potential for serious risk to the health, safety, or welfare of a subject; is purported or represented to be for use supporting or sustaining human life and presents a potential for serious risk to the health, safety, or welfare of a subject; Is for a use of substantial importance in diagnosing, curing, mitigating, or treating disease, or otherwise preventing impairment of human health and presents a potential for serious risk to the health, safety, or welfare of a subject; or otherwise presents a potential for serious risk to the health, safety, or welfare of a subject." The urine assay does not meet these criteria as it is noninvasive and merely tests levels of tenofovir in urine samples. Although test results will be shared with patients, which excludes it from the exempt category, no clinical decisions will be made based on the results. While the assay will be used to measure medication adherence, the collection of adherence information does not present a potential for serious risk to the health, safety, or welfare of the subject. Therefore the urine assay meets the criteria under the IDE.

**Nonsignificant Risk Medical Device study with additional details provided here:**

The non-invasive urine assay will be used to detect the absence or presence of tenofovir (the metabolite of TDF) in urine to improve adherence counseling. TDF is used in HIV treatment regimens worldwide and is also the only agent (in combination with emtricitabine) approved for pre-exposure prophylaxis (PrEP) worldwide. The threshold of the assay was designed to distinguish between people who have taken TDF within the prior four days (“adherent”) versus those who have not (“non-adherent”) taken TDF within the prior four days. Participants who are considered “adherent” by the assay in the intervention arm of PUMA will be informed of the result and continue to receive standard adherence counseling. Participants who are considered “non-adherent” by the assay will receive enhanced adherence counseling with positive messaging (detailed below).

The antibody that was developed against tenofovir for this novel assay is highly selective. As above, the assay has been demonstrated to have very high sensitivity and specificity in our recently concluded clinical validation studies against both the gold standard of measuring drug levels, LC-MS/MS, and the laboratory-based method of performing immunoassays (enzyme-linked immunosorbent assay or ELISA). Therefore, this test has a very low rate of false positivity and we have designed it to have a very low false negative rate. In the unlikely situation of false positive results (where the results indicate “adherent” when the participant is not taking their medication), participants will continue to receive standard adherence counseling. In the very unlikely event of false negative results (where the results indicate “non-adherent” when the participant is taking their medication) the participant will receive enhanced adherence counseling (which does not meet the definition of “significant risk”) in the intervention arm of PUMA. Therefore, participant access to standard adherence counseling will not be affected by a false positive result. We do not anticipate any adverse consequences for participants who receive enhanced adherence counseling due to being wrongly classified as non-adherent (a very rare event). The feedback and adherence counseling will be delivered in a supportive non-judgmental manner.

#### **9.4 Adherence Counseling Session (Intervention Arm Only)**

Participants in the PrEP2-BAY intervention arm will complete two individually delivered sessions via zoom designed to enhance intrinsic motivation and self-efficacy for maintaining adherence to PrEP and addressing the intersection of substance use and HIV risk. Session 1 focuses on supporting efforts of participants to continue taking PrEP adequately to achieve protection from HIV infection. Session 2 focuses on addressing the intersection of substance use and HIV risk. Counseling sessions will also reflect on results of the urine test collected and analyzed immediately prior to the session by the participant. The counselling intervention manual is also attached.

#### **9.5 Survey Collection**

The quantitative survey will be performed and collected using Redcap software either on the participants phone or home computer. The participant identification number will be inputted into the survey to allow linking of the survey to the participant's urine sample. The survey will take 20-30 minutes to complete and contains approximately 100 questions. The survey will be completed by the participant after each research visit.

#### **9.6 In-depth Interviews**

In-depth interviews will be conducted among 20 YMSM to assess acceptability, as well as to explore mechanisms by which the intervention motivated changes in adherence. We will use purposive sampling among participants in the intervention arm, with a goal to include 15 individuals who reported adherence challenges and 5 who did not report adherence challenges, as well as achieve a racially/ethnically and geographically diverse sample of respondents. Participants will receive an additional \$50 reimbursement for completing an interview.

#### **9.7 Early Termination of Study Participation**

Participants may voluntarily withdraw from the study for any reason at any time. The site investigators, with the approval of the Protocol Team, withdraw participants before their scheduled termination visit to protect their safety or staff safety, and/or if participants are unable or unwilling to comply with study procedures. Participants also may be withdrawn if the study sponsors, government or regulatory authorities (including the OHRP and US FDA), or IRB terminate the study prior to its planned end date. Study staff will record the reason(s) for all withdrawals in participants' study records.

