**YMSM have adherence challenges and a drop-off in adherence heralds future PrEP discontinuation.** In an analysis of data from the U.S. PrEP Demonstration Project, conducted between October 2012 and February 2015, for which SFCC was the largest site, we examined short-term adherence to PrEP using emtricitabine-triphosphate (FTC-TP) levels in dried blood spots (DBS). FTC-TP assesses adherence in the prior week similar to urine tenofovir (TFV) measurement. We found that 25% of participants had undetectable FTC-TP levels over the study duration, and a drop-off in short-term adherence heralded future PrEP discontinuation (adjusted hazard ratio: 6.3; 95% Confidence Interval (CI): 3.8-10.2). FTC-TP levels predicted future discontinuation more strongly than long-term adherence metrics (e.g. TFV-diphosphate levels in DBS). Younger (age<30) vs. older MSM had 2.5-fold higher odds of low FTC-TP (95% CI: 1.7-3.9).

**The POC urine immunoassay is sensitive, specific, and highly correlated with gold-standard metrics; low adherence via the assay identified MSM at risk of future HIV seroconversion.** Samples from a directly observed therapy (DOT) study (n=30), where

standard, LC-MS/MS (R01 AI143340 PI: [name]). The novel immunoassay was sensitive (94%), specific (99%), and the correlation was high (0.92,  $p < 0.001$ ). A cut-off of 1,500 ng/ml accurately classified 98% of patients who took a dose within the last 24 hours as adherent. The immunoassay has now been developed, validated against LC-MS/MS concentrations with high sensitivity and specificity, and packaged into a POC test with this cut-off (**Fig. 1**). Finally, in a secondary data analysis of a large PrEP demonstration project, the iPrEx-OLE study, we found that low vs. high urine TFV was associated with 14-fold higher odds of future HIV seroconversion (95% CI: 1.3-1197).

TDF/FTC was given to HIV-uninfected volunteers at 2, 4 and 7 doses per week, were used to compare urine TFV levels by the novel immunoassay with levels derived from the analytic gold

**Barriers to PrEP adherence in YMSM could be amenable to counseling; drug-level feedback can further enhance adherence counseling.** To assess barriers to non-adherence that could potentially be amenable to counseling, we analyzed preliminary data

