#### 5.2 Secondary Endpoint

Preliminary impact on adherence as assessed by tenofovir hair levels (long-term adherence): Change in tenofovir levels in hair from baseline and after 3 months of follow-up will be compared between the intervention and standard of care arm.

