## 9 STUDY PROCEDURES AND GUIDELINES

### 9.1 Recruitment and Consent:

This study involves two video (Zoom)/phone research visits for each of the 60 participants. Potential participants who are interested in participating in the study will contact the recruitment website/email address provided on recruitment notices on social networks. First, the study coordinator(s) will evaluate participants for eligibility for the study as per the inclusion criteria above. All participants will be informed of the purpose of the study, risks and discomforts involved, potential benefits, etc. Participants will be given as much time as necessary to consider study participation and are offered the opportunity to review the consent form on their own to provide adequate time to consider participation. The study team will engage the potential participant in a dialogue, using open-ended questions about the nature of the study or the experimental treatment, the risks and benefits of participating, and the voluntary nature of participation. Potential participants will be asked or shown a series of questions to assess their understanding of the study purpose, procedures, risks and benefits, as well as the voluntary nature of participation. Informed consent will occur remotely using the phone/zoom, and the signature via Docusign.

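### Section 9.7 permits withdrawal before month 3 for non-compliance, and the intervention arm has more procedures to decline, so month-3 hair can be lost unequally by arm and the secondary hair comparison can be biased

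*Combined protocol and SAP*

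**What the plan says.** Section 9.7 provides that site investigators, "with the approval of the Protocol Team, withdraw participants before their scheduled termination visit", for safety reasons "and/or if participants are unable or unwilling to comply with study procedures". The sentence lacks a modal verb. Because it requires approval and the next sentence is permissive, I read it as a power and not a duty. Reasons for withdrawal are recorded. The section does not define study procedures, and it does not say whether month-3 hair is still requested afterwards.

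Procedures by arm:

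- **Both arms.** "This study involves two video (Zoom)/phone research visits for each of the 60 participants" (9.1). Hair is self-collected and mailed at enrolment and month 3 (9.2). A survey of about 100 questions follows each visit (9.5).
- **Intervention arm only.** "Urine samples will be collected by the participant before or during the video visit only for participants in the intervention arm" (9.3), and "Participants in the PrEP2-BAY intervention arm will complete two individually delivered sessions via zoom" (9.4). The schedule places the urine test and counseling at Month 0 and Month 3.

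The trial is open-label (8.2). Under 5.2, the change in hair tenofovir "will be compared between the intervention and standard of care arm". The synopsis and 10.2 plan random-intercept models over the two time points. Neither gives an analysis population, a missing-data rule, a dropout allowance or a sensitivity analysis for this endpoint. (Section 10.2 names dried blood spots instead of hair. That is a separate matter, and I read these models as the ones intended for hair.)

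**The concern.** Someone who would post a hair sample but will not do the urine test or the counseling can be withdrawn under 9.7 if assigned to the intervention. In the control arm that person has no equivalent procedure to decline and would stay. The decision is discretionary and made with the arm known. If withdrawal also ends hair collection, the arms at month 3 are no longer the arms that were randomised.

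Acceptability is tabulated in the intervention arm alone, so hair is the trial's only controlled comparison, and the synopsis says the findings will lead to an application for a multi-city trial. If those lost were poorer adherers in a way not already visible in their baseline hair, an intervention with no effect could look helpful.

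**Working it through.** **Plan's own figure.** There is none to reproduce. The documents give no power, effect size or withdrawal rate for hair. The 82% power in the synopsis concerns acceptability and does not bear on this point.

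**Inputs.** From the documents: 40 intervention and 20 control participants, hair at two times, random-intercept models. Assumed: no true effect; loss in the intervention arm only, mainly 4 of 40 (10%), with 5% to 20% as the range; correlation r between baseline and month-3 log hair level of 0.5 or 0.7; true optimal adherence of 70% for the binary illustration. SD means the SD of log hair level.

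**Step 1: observed proportion.** With 70% adherent, 28 of 40 are adherent. Remove 4, varying how many of them are non-adherent:

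| Non-adherent among the 4 lost | Observed | Shift |
|---|---|---|
| All 4 | 28/36 = 77.8% | +7.8 points |
| 3 (75%) | 27/36 = 75.0% | +5.0 |
| 1.2 (30%, as in the arm) | 25.2/36 = 70.0% | 0 |
| None | 24/36 = 66.7% | -3.3 |

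The sign depends on whether those lost are less adherent than the rest of the arm.

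**Step 2: what a likelihood-based mixed model corrects.** With bivariate-normal levels, the bias in the intervention arm's month-3 mean is

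bias = (shift in observed month-3 mean) - r × (shift in baseline mean of those observed).

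- Loss driven by baseline level: the month-3 shift equals r times the baseline shift, so the bias is 0. At 10% loss, a completers-only mean would be off by +0.045 (r = 0.5) or +0.063 (r = 0.7).
- Loss driven by month-3 level (logistic, slope 1 per SD) at 10%: the completer shift is +0.091 and the baseline shift is r × 0.091. Bias = 0.091 × (1 - r²), which is 0.091 × 0.75 = +0.068 at r = 0.5 and 0.091 × 0.51 = +0.046 at r = 0.7.
- Loss of high month-3 levels: -0.068 and -0.046.
- Over 5% to 20% loss, low-month-3 selection gives about +0.02 to +0.13, and high-month-3 selection the mirror image.

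**Step 3: type I error.** Simulated trials of 40 versus 20 with no effect, 4 intervention values removed, and month 3 compared with adjustment for baseline (two-sided 5%):

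| Who is lost | Bias, r = 0.5 / 0.7 (SD) | Type I error |
|---|---|---|
| Random, or lowest 4 at baseline | 0 / 0 | about 5% |
| Graded towards low month-3 level | about +0.07 / +0.05 | about 6% |
| Lowest 4 at month 3 | about +0.15 / +0.10 | about 12% / 10% |

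The last row is a worst case, because month-3 levels are not known when the withdrawal decision is made.

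**Step 4: scale.** The standard error of the arm difference in change with 36 and 20 observed is √[2(1 - r)(1/36 + 1/20)], which is 0.279 at r = 0.5 and 0.216 at r = 0.7. The graded bias is then 0.068/0.279 = 0.24 or 0.046/0.216 = 0.21 of a standard error.

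**The case against.** The other side has several good points.

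- A reader might infer that the comparison *is* biased towards benefit, and might cite the Background's preliminary data, where "a drop-off in short-term adherence heralded future PrEP discontinuation" (adjusted hazard ratio 6.3). That result concerns stopping PrEP, not refusing study procedures. The study does not supply PrEP (section 7), and taking it is not listed as a study procedure. No passage links refusal of a test or session to adherence.
- A reader might also infer that the rule bites in one arm only. Control participants have visits, hair and surveys to refuse, so the exposure is unequal and not one-sided.
- Section 6.1 recruits people already prepared to give urine, so many who would refuse the test should not enter either arm.
- The second test and session fall at the Month 3 visit, alongside the final hair sample. Early withdrawal would therefore be triggered mainly at Month 0, although the synopsis spacing of about two to three months leaves some slack.
- Hair is a secondary, preliminary endpoint of a pilot. Withdrawal reasons are recorded, and the DSMB sees retention by group (11.3).

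All of this limits the certainty and size of the problem. It does not close the gap: monitoring shows an imbalance without correcting it, and the plan does not say whether hair collection continues after withdrawal. A direction towards benefit remains plausible, since the extra procedures are a drug-level check and a discussion of the result, and 9.8 acknowledges that counseling may embarrass or worry participants.

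**Conclusion.** The concern holds as a risk: the hair comparison can be biased by unequal loss arising from 9.7. The documents do not show that it will be, or in which direction. Bias towards benefit needs three things together: withdrawal under this rule more often in the intervention arm, hair not collected afterwards, and those lost being poorer adherers beyond what their baseline hair predicts.

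With 4 of 40 lost and no true effect, both assumed, the bias runs from 0 through about +0.05 to +0.07 SD to a worst case of +0.10 to +0.15 SD, where type I error is 10 to 12%. It turns negative if better adherers are lost. These figures also rest on the assumed correlations of 0.5 and 0.7. The change should be made because it is cheap and protects the only between-arm comparison.

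**What to change.** 1. Amend 9.7 so that declining the urine test or counseling ends those procedures only. The safety provision is not affected by this point.
2. State that the month-3 mailed hair sample and survey are still requested from everyone randomised, unless they withdraw consent to data collection. Hair is posted from home, so it does not depend on attending a session. Wherever it is returned, this source of bias disappears.
3. Analyse hair by randomised arm, and report the number and reasons for missing month-3 hair in each arm.
4. Add one sensitivity analysis with missing month-3 hair set to sub-optimal (binary) or to the assay limit (continuous), first in the intervention arm only and then in both arms.

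Cost: a short amendment, a few follow-up envelopes and one table.

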#### **9.8 Risks to Participants**

There is potential for loss of confidentiality in all research, but risk to participants will be minimized by training all staff in the ethical conduct of research. Data for the participants in this study will be obtained from the medical record, or from behavioral questionnaires administered (via tablet or personal electronic device).

If data related to illicit drug use were disclosed due to a loss of confidentiality, there could be risk of criminal justice involvement.

There is no substantial risk for urine collection or performance of the urine point of care test.

Participants may feel slight pulling at the scalp when using scissors to collect a hair sample.

Participants will be asked questions about their sexual behavior that may make them feel uneasy. Participants do not have to answer any question that they do not want to and can stop answering the questions at any time. Participants may also become embarrassed, worried, or anxious when being counseled about PrEP.

Strict protection of the data will be maintained through using password protected databases. There may be risks of discrimination or other personal problems from being in this study. The most common risks we know about are family or friends worrying, getting upset or angry, or assuming that you are HIV-infected and treating you unfairly as a result. The study staff will take the same steps to protect participant privacy. The participant may be embarrassed or feel uncomfortable with some of the questions that are asked during the study. The participant does not have to answer any questions that make them uncomfortable.

## **9.10 Benefits to the Subject or Future Benefits**

The participant may receive no immediate benefits from the research study. It is possible that the participant may improve their PrEP adherence behavior, which could lead to decreased HIV risk. The participant may also feel satisfaction at having contributed to knowledge within a health field.

Prior to conducting any study-related activities, written informed consent and the Health Insurance Portability and Accountability Act (HIPAA) authorization must be signed and dated by the subject. If appropriate, assent must also be obtained prior to conducting any study-related activities.

## **10 Data management and analysis**

### **10.1. Data management**

Questionnaire data will be collected online using Redcap and stored in password-protected databases. All study staff will be trained in Good Clinical Practice (GCP) and will have received additional training about maintaining confidentiality.

All assessments (questionnaires, CRFs) will be identified by only a coded number to maintain participant confidentiality. All study staff will be trained in Good Clinical Practice (GCP), Human Subjects Protection (HSP) and will have received additional training about maintaining confidentiality. Only study staff will have access to individually identifiable study data.

Audio-recorded qualitative interviews will be recorded onto digital media using a portable recorder that records directly into computer readable format and can be transferred from the recorder and stored in an encrypted volume that is then stored on a secure computer or burned on a DVD which will be stored in a locked cabinet. The data will be transferred via USB cable to a password-protected, encrypted volume created on a laptop computer. Only study personnel will have access to the password. A copy of the encrypted volume would be stored on secured servers at one of the research institutions for study team members at different research sites to access. The encrypted volume will be opened (mounted) only when it is being used for analysis purposes. At all other times, the encrypted volumes containing the data will remain closed (dismounted) and thereby encrypted. Because the data are stored in an encrypted format, the risk of unauthorized access is very low.

